11.1.1 Populations Analysed

The primary analysis based on the assessment of the safety and tolerability of the study drug (primary objective) will be performed on the Safety Analysis Set.

The efficacy analysis will be performed on the ITT and PP sets.

11.1.2 Reasons for Exclusion from the Analyses

Any major protocol deviation (see Section 13.1.2 for definition) will be described and its impact on inclusion in each analysis population (PP, safety and PK populations) for any subject will be specified. The final list of protocol deviations impacting the safety, ITT and PP populations will be reviewed prior to database lock. The list may be updated, up to the point of database lock, to include any additional major protocol deviations impacting inclusion in the PP population.

11.2 Sample Size Determination

It is anticipated that a total of up to 55 subjects will be recruited, up to 15 subjects in Part A and up to 40 subjects in Part B. This is considered appropriate for an exploratory study and it is not based on formal statistical sample size calculation. In the event subjects do not complete treatment due to any reasons other than exceedance of organ dose limits or treatment related safety issues, additional subjects may be recruited as replacements to ensure an adequate sample size in the “per protocol set” for safety evaluation. Subjects with noninterpretable dosimetry scans may be replaced upon agreement of the investigator and the sponsor.

For Cohorts 3 and 6 in Part B, to detect a difference between two peptide doses within the same cohort, the total sample size of eight is calculated. Assuming 30% standard deviation of the paired difference, there is 80% power to detect a 2-fold-change, and 99% power to detect a 3-fold change at a 2-sided alpha of 0.05.

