3.1.2 Part B Design

Part B is a dose escalation both of peptide mass and radioactivity. Up to eight cohorts will be enrolled as described below, see Figure 13.

[figure not shown]
Part B will encompass radioactivity and peptide mass dose escalation as well as intra-individual peptide mass dose evaluation. It consists of up to eight cohorts. In each cohort, each subject will receive three cycles of the defined radioactivity and peptide mass dose of ¹⁷⁷Lu-OPS201

(see Section 6.2, Table 11). Each cycle will be 8 (+2) weeks apart. In case of AEs which are not adequately recovered, a further 4 weeks can be added between dosing.

After the three core-treatment cycles, up to two additional cycles of ^{177}Lu -OPS201 can be administered if the subject continues to meet the criteria outlined in Section 6.4.2 and the subject has clinical benefit (defined as CR, PR or SD). The additional cycles are optional and must be discussed with the sponsor before administration.

The population of Cohorts 3 and 6 will enrol eight to 10 subjects to ensure a minimum of eight completed subjects. All remaining cohorts (1, 2, 4, 5, 7 and 8) will enrol three to five subjects to ensure a minimum of three completed subjects per cohort (see Section 3.3). A completed subject is defined as one who has received at least 3 cycles of study treatment or fewer than 3 cycles if one of the following has occurred: exceedance of organ dose limits, treatment-related safety issues or disease progression.

Figure 13 Study Design - Part B

DRB=data review board; GBq=gigaBecquerel; SRC=safety review committee.

Each cohort consists of three cycles of treatment. Cohort 2 will not be conducted if 700 μg or 1300 μg peptide mass is shown to be optimal. Cohorts 7 and 8 will not be conducted if 1300 μg peptide mass is seen to be too high. Cohorts 3 and 6 require 10 subjects for eight to be completed. All other cohorts are three to five subjects (minimum of three subjects to be completed).

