3.1.3 Justification for Part B Design

In animal experiments, no saturation of the sstr2 was observed when higher peptide mass doses were administered in a xenograft mouse model.[39] Nevertheless, the effect of the increasing peptide mass dose and the peptide mass at which lesion receptor saturation occurs in humans is unknown. The extrapolation from animal experiments may be limited by the fact that, in these

xenografts, receptor density was relatively high in comparison to normal distribution of receptors in the mouse.

Receptor saturation by the peptide is predicated on:

- (a) the number of receptors in nontumoural tissue (physiological expression) and
- (b) tumour burden and related sstr2 density (total receptor burden).

Regardless of tumour type, the higher the receptor burden the more peptide maybe required before saturation occurs. It is therefore important that the peptide masses being studied in this protocol are evaluated for sstr2 saturation. Hence Cohorts 3 and 6 will evaluate the peptide mass and specifically if receptor saturation has occurred, starting with 300 µg for Cycle 1, then increasing to 700 µg and 1300 µg respectively for Cycle 2 before repeating the 300 µg dosing for Cycle 3 (see [Figure 13](#)). Thus, the tumour-to-background dose ratio, and the tumour-to-bone-marrow dose ratio, using imaging dosimetry, can be evaluated in the same subjects. In these cohorts, administering 4.5 GBq/cycle, which was shown to be tolerated in Part A of the study, will allow comparison of intra-subject variability of the uptake due only to the peptide mass. It also allows Cohort 3 to start in parallel to Cohort 1 which is the next logical increase in dosing at 300 µg (6 GBq per cycle) following Part A.

The other cohorts in Part B will be initiated in a staggered manner after gaining experience with previous cohorts, thereby allowing safer investigation at higher radioactivity and/or higher peptide mass dose. If tumour sstr2 saturation is observed, then the lower peptide dose will be confirmed. Therefore, Cohorts 7 and 8 will be cancelled if the peptide saturation is seen in Cohorts 3 and/or 6. Similarly, Cohort 2 may be cancelled if a peptide mass dose range of 700 µg to 1300 µg is found to be optimal.

Subject numbers

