Cohorts 3 and 6 will require 8 subjects to ensure there is sufficient power to demonstrate any tumour sstr2 saturation. Therefore 10 subjects will be enrolled to obtain a minimum of 8 completed subjects. All remaining cohorts (1, 2, 4, 5, 7 and 8) will enrol three to five subjects to obtain a minimum of three completed subjects per cohort.

Hence, it is anticipated that 10 subjects will be enrolled in Cohorts 3 and 6, and five subjects will be enrolled in Cohort 1, so the end-point can be achieved in these initial three cohorts rapidly (total of 25). To maintain the subject numbers to a maximum of 40 in Part B, if all remaining cohorts are utilised (total of five), each will have three subjects enrolled (total of 15).

Change in eligibility criteria for Part B

To ensure sufficient precision for the imaging dosimetry (specifically in Cohorts 3 and 6, but also for the whole study), eligibility will require a minimum of two lesions ≥ 20 mm in diameter. Tumour dosimetry should be performed on tumour lesions identified by the imaging core laboratory and on no more than five lesions (maximum two per organ, size ≥ 20 mm diameter, accessible for dosimetry). Furthermore, this ensures the modelling is based on a minimal total receptor burden.

Infusion rate

The i.v. infusion of ^{177}Lu -OPS201, should be at a rate of 10 mL/h over 120 minutes (see Section 6.2.1).

Investigators are advised that prophylaxis may be considered if the patient is thought to be at increased risk of infusion-related reactions as per the site's standard of care (see also 6.3.3 and Section 6.3.4). Appropriate treatment should be administered should an infusion-related reaction occur including somatostatin analogues. The administered radioactivity and mass dose follows the escalation scheme (see Section 6.2).

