11.3 Significance Testing and Estimations

As this is a descriptive safety and tolerability/efficacy study, no formal statistical testing will be carried out.

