11.6 Interim Analyses/Safety Review Committees/Data Review Boards

Dosimetry evaluation will be performed on an ongoing basis. After the first six subjects included have completed the study Part A (EOCT/EW Visit) an SRC meeting will be held before exposing the remaining subjects to the entire number of planned administrations. Safety data obtained until 8 weeks after the last administration of the 6th subject will be evaluated during this SRC. Prior to Part B, the SRC will review the safety and dosimetry data of the first six subjects included in Part A.

For Part B, a DRB meeting will be held to review the safety and radiation exposure data and decide whether to proceed with the enrolment of the next cohort dose level and the cumulative radioactivity within a cohort. Each dose escalation (both peptide and radioactivity) will be carefully evaluated by a DRB (see [Figure 13](#) and [Appendix 3](#)).

In addition, the SRC/DRB can be convened at any time during the trial to discuss potential safety issues. The data set to be reviewed by the SRC/DRB is specified in a specific charter.

A first interim analysis will be conducted at the cut-off date of 27 September 2019 to inform the design of the chemotherapy combination study which has been added to the investigational plan.

A second interim analysis of Part B data will be conducted at the EOCT/EOAC/EW (whichever occurs last) after completion of Cohorts 3 and 6. This will provide confirmation of the peptide dose to allow future studies to be developed. It will also confirm if Cohorts 2 or 7 and 8 will be initiated.

A third interim analysis, including all dosimetry, safety and efficacy data, will be performed after the EOCT/EOAC/EW (whichever occurs last) when the two study parts are completed.

The interim analyses may be combined based on the overall study status and subject accrual.

The final analysis will be performed at the end of the 2-year long-term follow-up period.

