Cumulatively excreted radioactivity in urine (unit: MBq) will be listed by study part, cohort (part B only), radioactivity level adapted or not (part B only), subject, cycle and time period.

Descriptive statistics, including geometric mean and geometric Coefficient of Variation (CV), will be presented by study part, cohort (part B only), cycle and time period on the ITT Set.

(b) Radiation Dosimetry

- Organs receiving the highest absorbed dose (unit: Gy).

All organs with their absorbed dose will be listed by study part, cohort (part B only), radioactivity level adapted or not (part B only), cycle, organ and subject on the ITT- DAS, and highest dose will be flagged.

- Specific absorbed dose to the lesions selected for the dosimetry evaluation (unit: Gy/GBq).

Specific absorbed dose to the lesions selected for the dosimetry evaluation will be listed by study part, cohort (part B only), radioactivity level adapted or not (part B only), subject, cycle and lesion number. Descriptive statistics, including geometric mean and geometric Coefficient of Variation (CV), will be presented by study part, cohort (part B only), cycle and lesion location on the ITT- DAS and PP-DAS. Descriptive statistics will also be presented on combined lesions on the PP-DAS population.

- Specific absorbed dose per organ (unit: Gy/GBq).

Specific absorbed dose per organ will be listed by study part, cohort (part B only), radioactivity level adapted or not (part B only), subject, cycle and organ. Descriptive statistics, including geometric mean and geometric Coefficient of Variation (CV), will be presented by study part, cohort (part B only), cycle and organ on the ITT- DAS and PP-DAS.

- Ratio of Specific absorbed dose per organ and lesion.

Ratio of specific absorbed dose at visits (e.g. visit 2 relative to visit 1, visit 3 relative to visit 1, visit 2 relative to visit 3, etc..) will be calculated per organ and per lesion and by study part (Part A and B), and by each cohort (applies to part B only), radioactivity level adapted or not (applies to part B only), subject, cycle and organ. Descriptive statistics, including geometric mean and geometric Coefficient of Variation (CV), will be presented by study part, cohort (part B only), cycle and organ on the PP-DAS.

Boxplots representing the ratio of specific absorbed doses between visits by organ and lesion will be produced.

- Tumour average/kidney ratio

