DRB-B	Cohort 3 First three subjects, EOC-2	Start Cohort 4 with 6 GBq?	If >65% DLTs in Cohort 3 then NO to Cohort 4. If >33% and <67% DLTs in Cohort 3 Cycle 2 then wait for three more subjects in Cohort 3 Cycle 2 and re-evaluate. Otherwise start Cohort 4. Cohort 4 will not start recruiting until Cohorts 1, 3 and 6 are fully recruited
DRB-C	Cohort 4 EOC-1	Start Cohort 5? Continue Cohort 4?	If >33% DLTs in Cohort 4 then NO to Cohort 5. If >33% DLTs in Cohort 4 then STOP. Evaluate peptide mass dosing and lesion receptor saturation. Evaluate next cohort to start and activity dosing.
DRB-D	Cohort 6 EOC-3 All subjects Cohort 4 EOC-1	Start Cohort 7?	If >33% DLT in Cohort 6 Cycle 2 NO to Cohort 7 AND If lesion receptor saturation in Cohort 6 Cycle 2, then no to Cohort 7 AND If >33% DLTs and <67% DLTs in Cohort 4 and receptor modelling suggests Cohort 7 mass dose safer, then start Cohort 7, otherwise no.
DRB-E	Cohort 6 EOC-3 All subjects Cohort 5 EOC-1	Start Cohort 8?	If >33% DLT in Cohort 6 Cycle 2 NO to Cohort 8 AND If lesion receptor saturation in Cohort 6 Cycle 2, then no to Cohort 8 AND If >33% DLTs <67% DLTs in Cohort 5 and receptor modelling suggests Cohort 8 mass dose safer, then start Cohort 8, otherwise no.
DRB-F	Cohort 1 EOC-3 and Cohort 3 EOC-3 and Cohort 5 EOC-1	Start Cohort 2?	If mass dose modelling suggest 300 ug is optimal AND If >33% DLTs in Cohort 1, AND If >33% DLTs in Cohort 5 Start Cohort 2

DLT=dose limiting toxicity; DRB=data review board; EOC=end of cycle; GBq=gigabecquerel.

Note: At each DRB, safety data available from all cohorts will be evaluated to inform decision making.

a although the DRBs are written in alphabetical sequence this is not a chronological order; each one will be conducted when data becomes available which is dependent on subject recruitment. An ad-hoc DRB can be called to ensure continuity of dosing. Although three completed subjects are required for each completed cycle for evaluation, all available subject data in that cohort will be used (e.g. If five subjects are enrolled and all five complete the end of a cycle prior to the DRB, then all five sets of data will be evaluated).

This cumulative activity in the cohort being evaluated will be determined by the following DLT rules:

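### The 80%/99% power stated for eight subjects in Cohorts 3 and 6 does not follow from its own inputs by a paired t-test unless the SD of the tested contrast is about 0.26 on log10; variable, scale, contrast and test are not given

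*Protocol*

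**What the plan says.** Protocol 11.2 first says that the overall total of up to 55 subjects is exploratory and rests on no formal calculation. For Cohorts 3 and 6 it then says that eight is calculated, for a comparison of two peptide doses within a cohort at two-sided alpha 0.05: "Assuming 30% standard deviation of the paired difference, there is 80% power to detect a 2-fold-change, and 99% power to detect a 3-fold change". SAP 1.3.7 repeats the sentence and adds nothing on scale or method.

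Protocol 3.1.3 gives the purpose: "Cohorts 3 and 6 will require 8 subjects to ensure there is sufficient power to demonstrate any tumour sstr2 saturation". It plans to enrol 10 per cohort to obtain at least eight completed. Under Protocol 3.1.2 a completed subject has received three cycles, "or fewer than 3 cycles if one of the following has occurred: exceedance of organ dose limits, treatment-related safety issues or disease progression".

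Both cohorts give 300 µg in Cycles 1 and 3 and the higher mass (700 or 1300 µg) in Cycle 2.

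The result feeds later decisions. Protocol 3.1.3: "Cohorts 7 and 8 will be cancelled if the peptide saturation is seen in Cohorts 3 and/or 6". SAP 3.2.19, Table 9, DRB-D: "If lesion receptor saturation in Cohort 6 Cycle 2, then no to Cohort 7". Protocol 11.6, on the interim analysis after these cohorts: "It will also confirm if Cohorts 2 or 7 and 8 will be initiated".

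On analysis, Protocol 11.3 says "no formal statistical testing will be carried out". The nearest planned output is the descriptive set of between-visit ratios of specific absorbed dose in SAP 3.2.2 ("visit 2 relative to visit 1, visit 3 relative to visit 1, visit 2 relative to visit 3"), which is not linked to the power statement.

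**The concern.** A standard deviation of 30% paired with fold-changes has no meaning until a scale is chosen, and the answer depends heavily on it. A 2-fold change is 0.301 on log10 and 0.693 on the natural log. Against an SD of 0.30 that is a standardised effect of 1.00 or 2.31. With eight pairs the first gives power well short of 80% and the second gives near certainty. A reader who takes 30% as an ordinary CV will think that the cohorts can detect much smaller changes than 2-fold. A reader who takes it as a log10 SD will trust an 80% that the t distribution does not support.

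At stake is what an absence of visible saturation would mean when Cohorts 2, 7 and 8 are considered. The power sentence is the only visible statement of how large a change eight subjects can show.

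**Working it through.** **Inputs.** n = 8, two-sided alpha 0.05, SD of the paired difference 30%, effects 2-fold and 3-fold (Protocol 11.2, SAP 1.3.7). The scale is not given, so each reading is tried.

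**1. Reproducing the stated figures.** Normal approximation on log10, SD 0.30: power = Φ(log10(fold) × √8 / 0.30 − 1.96).
- 2-fold: 0.3010 × 2.828 / 0.30 = 2.838; Φ(0.878) = 81.0%.
- 3-fold: 0.4771 × 2.828 / 0.30 = 4.498; Φ(2.538) = 99.4%.
- Inverse, 80% at 2-fold: n = ((1.960 + 0.842) × 0.30 / 0.3010)² = 7.8, rounded up to 8.

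This matches, but the normal approximation ignores estimation of the SD on 7 degrees of freedom (critical value 2.365, not 1.960).

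**2. Exact paired t-test, n = 8** (noncentral t, 7 df, noncentrality = effect × √8 / SD). At 80% power the standardised effect must be 1.156, so the detectable fold is 10^(1.156 × SD) on log10 or exp(1.156 × SD) on the natural log.

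| Reading of the SD | 2-fold | 3-fold | 80% power at |
|---|---|---|---|
| log10 SD 0.30 | 68.4% | 96.9% | 2.22-fold |
| natural-log SD 0.30 | 99.98% | >99.99% | 1.41-fold |
| CV 30% (natural-log SD 0.2936) | 99.99% | >99.99% | 1.40-fold |
| log10 SD 0.26 | 80.1% | 99.3% | 2.00-fold |

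**3. SD that makes the stated pair right.** 0.3010 / 1.156 = 0.2604 on log10, which is 0.600 on the natural log; CV = √(exp(0.600²) − 1) = 66%.

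**4. A contrast that could give that SD.** Suppose 0.30 on log10 is the SD of one cycle-to-cycle difference, with independent, equal within-subject errors of variance σ². Then 2σ² = 0.09. Cycle 2 minus the mean of Cycles 1 and 3 has variance 1.5σ² = 0.0675, so SD = 0.30 × √0.75 = 0.26. The exact t-test on eight subjects gives 80.2% and 99.3%.

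**5. Number of pairs, log10 SD 0.30, exact t, 2-fold.** 7 pairs: 60.3%. 8: 68.4%. 9: 75.1%. 10: 80.6% (3-fold 99.3%).

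**6. Illustration only.** If the variable were tumour uptake or absorbed dose and the change a fall, the 80%-power folds would be losses (1 − 1/fold) of 55% (log10 SD 0.30), 50% (log10 SD 0.26) or 29% (natural-log SD or CV 30%). With an observed ratio of 1.0, the 95% lower limit would be 0.56, 0.61 or 0.78.

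**The case against.** - **The design has its own route to 80%/99%.** The 300 µg dose is repeated in Cycle 3, and comparing Cycle 2 with the mean of the two 300 µg cycles returns the stated pair by exact t (step 4). This stands as a possibility, so 68%/97% cannot be called the true power. It needs assumptions that the documents do not state, and the SD of that contrast would be 0.26, not the 30% printed.
- **Ten are enrolled.** Ten pairs give 80.6%/99.3% on log10 SD 0.30. But the power is stated for eight, and eight completed is all that the plan secures. A subject who stops after Cycle 1 for a listed reason counts as completed and gives no pair. Protocol 11.2 allows replacement for uninterpretable dosimetry scans, which covers part of this loss.
- **Other settings come close.** One-sided exact t on eight pairs gives 81.7%/99.1%, and two independent groups of four at CV 30% give 79.4%/99.1%. The text says two-sided and paired, so neither fits. They do show that a log10 origin is inferred from a match and not documented.
- **30% may be a per-measurement CV.** The text says it is the SD of the paired difference. Even so, with independent measurements (natural-log SD of the difference 0.415), 2-fold power would be about 98%, not 80%.
- **No test is planned and the study is exploratory.** True, and Protocol 11.4 already allows 95% confidence intervals where appropriate. SAP 3.1.7.4, Modelling, is listed but its text is not visible, and Table 9 refers to receptor modelling. This lowers the weight of the point but does not make the stated figures follow from their inputs.

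A reader might infer that the cohorts are underpowered, or that losses of up to about half would be missed. The documents support neither: the scale is unknown, one reading gives very high power, and the power statement names neither uptake nor a direction. Protocol 3.1.3 speaks of tumour-to-background and tumour-to-bone-marrow dose ratios, and Protocol 2.3 expects peptide mass to improve the tumour-to-background ratio.

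**Conclusion.** The power statement is incomplete and, taken as written, is not what an exact paired t-test on eight pairs delivers. It is about 12 points too high at 2-fold and 2 points at 3-fold if 0.30 is a log10 SD. It is far too low at 2-fold if 30% is a natural-log SD or CV. It is right only for a contrast SD of about 0.26 on log10.

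The claim of sufficient power for any saturation holds on no reading: the change detectable with 80% power is about 1.4-fold at best and 2.2-fold at worst.

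These figures assume approximately normal log differences and eight evaluable pairs. They do not show which calculation the sponsor ran, and they do not show that any decision on Cohorts 2, 7 or 8 would be wrong. This should be corrected, with limited practical weight.

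**What to change.** In Protocol 11.2 and SAP 1.3.7, name the variable, the scale, the contrast (Cycle 2 versus Cycle 1, or versus the mean of Cycles 1 and 3), the SD of that contrast and the test. Count n as subjects with evaluable dosimetry in every cycle compared. Then state the power from the t distribution for n = 8, using the line that applies:

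- contrast SD 0.30 on log10: 68% for 2-fold, 97% for 3-fold, 80% at about 2.2-fold;
- natural-log SD or CV 30%: above 99.9% for 2-fold, 80% at about 1.4-fold;
- contrast SD 0.26 on log10 (CV about 66%): keep 80% and 99%, and replace the 30% with this SD.

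In Protocol 3.1.3, replace the reference to any saturation with the resulting detectable fold-change. Optionally, add a t-based 95% interval (n − 1 degrees of freedom) to the geometric mean visit ratios for Cohorts 3 and 6 in SAP 3.2.2.

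Cost: three sentences, and one extra table column if the interval is added. Enrolment, visits and data collection do not change.

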11.3 Significance Testing and Estimations

As this is a descriptive safety and tolerability/efficacy study, no formal statistical testing will be carried out.

11.4 Statistical/Analytical Methods

Statistical analyses will be performed by external contract research organisations (CROs), managed by the sponsor’s Biometry Department.

Details of the statistical analysis are specified in the SAP.

The statistical analyses will be conducted using SAS (v9.2 or later).

Primarily, all variables will be analysed descriptively, as follows:

- Mean, standard deviation, median and range for continuous variables
- Median, range and frequency distribution for discrete (ordinal) variables
- Frequency distribution for nominal variables.

Secondarily, the variables descriptive statistics will be presented by study part. If appropriate, results for total, Part A+B will be presented. In the event of dose escalation, study Parts A and B will be compared using nonparametric tests. The test results will be interpreted in an exploratory manner. 95% confidence intervals will be estimated as appropriate.

Data collected during the Long-term Follow-up will be analysed by means of a survival analysis (Kaplan-Meier method) with the respective plots and descriptive summaries.

